2.4.1.4 Dose reductions, interruptions or permanent discontinuations

The number of patients who have dose reductions, permanent discontinuations, or interruptions, and the reasons, will be summarized separately for each of the study treatment components.

‘Dose interrupted’, and ‘Dose permanently discontinued’ fields will be used to determine the dose reductions, dose interruptions, and permanent discontinuations, respectively.

The corresponding fields ‘Reason for dose change/dose interrupted’ and ‘Reason for permanent discontinuation’ will be used to summarize the reasons.

A dose change is either a ‘change in prescribed dose level’ or an ‘error’. For the latter, actual dose administered/total daily dose is different from the prescribed dose.

For the purpose of summarizing interruptions and reasons, in case multiple entries for interruption are entered on consecutive days with different reasons, these interruptions will be counted as separate. However, if the reason is the same in this mentioned multiple entries on consecutive days, then it will be counted as one interruption.

Dose reduction: A dose change where the prescribed dose level is lower than the previous prescribed dose level or where the actual dose administered/total daily dose is lower than the calculated dose amount based on the prescribed dose. Only dose change is collected in the eCRF. Number of reductions will be derived programmatically based on the change and the direction of the change.

Dose interruption: Actual dose administered equal to zero, between the first and last non-zero doses, following a non-zero actual dose administered. Dose interruption is collected as such in the treatment page eCRF. Number of dose interruptions and corresponding reason will be summarized. A patient with continued interruptions and no return will be considered as a permanent discontinuation.

Missing data: If dose is recorded but regimen is missing or entered as ‘none’, it is assumed that the investigational drug was taken as per-protocol.

In some cases the total dose administered may not be the same as the total prescribed dose - for example when the dose is prescribed by BSA (mg/m²) even though the total dose administered in (mg). In such cases there may be variations in the administered dose due to variations in BSA.

2.4.1.5 Compliance

Compliance to the study treatment will be summarized in terms of the RDI or percentage of patients who took a predefined percentage of the number of prescribed doses. The predefined RDI categories are < 0.5 , $\geq 0.5 - < 0.75$, $\geq 0.75 - < 0.9$, $\geq 0.9 - < 1.1$ and ≥ 1.1 . The number and proportion of patients falling in each category will be presented.

2.4.2 Prior, concomitant and post therapies

Summaries and listings of prior and post treatment anti-neoplastic treatments will be presented by treatment group and overall, using the FAS following the general analysis conventions defined under [Section 2.1](#).

Prior anti-neoplastic therapy

The number (%) of patients who received any prior anti-neoplastic medication will be summarized and listed. The summary of prior anti-neoplastic medications may include the total number of regimens (note: there can be more than one medication per regimen), setting at last medication, time (in days) from last treatment to progression, best (hematological/cytogenetic/molecular) response at last treatment (defined to be the best response during the last treatment regimens recorded), duration (in months) of last response (last response is the response at last medication) and reason for discontinuation at last medication. The last medication is defined based on the last start date of all prior regimen components. Prior anti-neoplastic medications will also be summarized by Anatomical Therapeutic Chemical (ATC) class and preferred term (PT).

The summary and listing of prior anti-neoplastic surgery may include prior surgery, procedure at last surgery, and residual disease at last surgery.

The summary and listing of prior anti-neoplastic radiotherapy may include the radiotherapy locations (including all locations recorded for each patient), setting at last radiotherapy, and whether last radiotherapy was 30% of bone marrow.

Anti-neoplastic medications will be coded using the WHO Drug Dictionary (WHO-DD); anti-neoplastic surgery will be coded using MedDRA. Details regarding MedDRA and WHO-DD version will be included in the footnote in the tables/listings.

Post treatment anti-neoplastic therapy

Anti-neoplastic therapies since discontinuation of study treatment will be listed by ATC and PT.

Concomitant medications

Concomitant therapy is defined as any intervention (therapeutic treatment and procedure) other than the study treatment administered to a patient coinciding with the study treatment period. Concomitant therapy includes medications (other than study drugs) starting on or after the start date of study treatment or medications starting prior to the start date of study treatment and continuing after the start date of study treatment. Concomitant medications will be coded using the WHO Drug Reference Listing (DRL) dictionary that employs the WHO ATC classification system.

All concomitant therapies and significant non-drug therapies will be summarized and listed using the safety set. Any concomitant therapies and significant non-drug therapies starting and ending prior to the start of study treatment or starting more than 30 days after the last date of study treatment will be flagged in the listing.

2.5 Analysis supporting primary objective(s)

There are three parts in the study.

The primary objective for Part 1 is to evaluate the efficacy of NIR178 in combination to PDR001 in patients with selected advanced solid tumors and DLBCL.

The primary objective for Part 2 is to assess the efficacy of several continuous and intermittent dosing schedule of NIR178 in combination with PDR001 in NSCLC.

The primary objective for Part 3 is to further evaluate the efficacy of intermittent or continuous dosing schedules (if selected) of NIR178 in combination with PDR001 in one or two selected treatment indications based on the emerging data from part 1 and part 2.

The reporting of efficacy analyses for respective parts will follow the general analysis conventions defined under [Section 2.1](#).

2.5.1 Primary endpoint(s)

The variable used to evaluate the primary objective is overall response rate (ORR), defined as the proportion of patients with best overall response (BOR) of complete response (CR) or partial response (PR), as per local review and according to RECIST v1.1 (see Protocol Appendix 2 for details) for solid tumors, [Cheson et al \(2014\)](#) for DLBCL, or PCWG3 criteria for mCRPC (see Protocol Appendix 5 for details).

2.5.2 Statistical hypothesis, model, and method of analysis

2.5.2.1 Part 1

This part will contain thirteen groups: (1) RCC IO naive at NIR178 160 mg BID, (2) RCC IO naive at NIR178 240 mg BID, (3) RCC IO pretreated at NIR178 240 mg BID, (4) pancreatic cancer at NIR178 160 mg BID, (5) urothelial cancer at NIR178 160 mg BID, (6) HNSCC IO naive at NIR178 160 mg BID, (7) HNSCC IO pretreated NIR178 160 mg BID, (8) MSS CRC RAS wildtype NIR178 160 mg BID, (9) MSS CRC RAS mutant NIR178 160 mg BID, (10) TNBC at NIR178 160 mg BID (11) melanoma IO pretreated NIR178 160 mg BID, (12) DLBCL at NIR178 160 mg BID, and (13) and mCPRC at NIR178 240 mg BID.

Note: The efficacy data from the Non-HNSCC patients, MSS CRC patients with unknown RAS status and melanoma IO naive patients will not be included in the statistical model. The efficacy data from any new treatment indications added to the existing 13 groups before the study closure (as a consequence of Protocol Amendment 5) that qualify the criteria for Part 1 may be used to inform the model.

All doses are given in combination with PDR001 400 mg Q4W. An adaptive Bayesian design ([Neuenschwander et al 2016](#)) will be used to assess activity of treatment in terms of overall

response rate (ORR) within each and across treatment indications. The design of the trial adapts to the data that are accumulated in the trial in such a way as to accommodate three possibilities:

- Scenario A: ORR is similar across treatment indications
- Scenario B: ORR is similar for some treatment indications and different in others
- Scenario C: The various treatment indications have distinct ORR

The pre-specified analysis is adaptive in the sense that when response is similar across all treatment indications (Scenario A), then it borrows information from across all the various treatment indications. In cases when few of the treatment indications have similar ORR (Scenario B), the model provides more precise estimates of ORR rates for the treatment indications that have similar response rates by allowing to borrow information only across these treatment indications. In the other possibility when the various treatment indications have distinct anti-tumor activity (Scenario C), the design allows little/no borrowing of information across treatment indications. In this case the trial will be similar to traditional stratified analysis.

A hierarchical model (HM) will be used to analyze the binary data to facilitate the borrowing as specified above. Response rates (π_j) will be inferred for treatment indication j ($= 1, \dots, J=13$). For each treatment indication j , the number of responders follows a binomial distribution;

$$r_j \sim \text{Bin}(n_j, \pi_j)$$

We further let the parameters $\theta_j = \log(\pi_j / (1 - \pi_j))$ (logistic transformation) be either exchangeable with few of the treatment indications, or non-exchangeable with any of them. Based on the number of strata in this trial, we allow for two exchangeability distributions, which, for example, account for the case where a few treatment indications show no efficacy and others are promising. Thus, for each treatment indication j , three possibilities arise, with respective probabilities $p_j = (p_{j1}, p_{j2}, p_{j3})$, as follows:

1. With probability p_{j1} (probability group j belongs to exchangeability set 1) θ_j follows a normal distribution with exchangeability parameters μ_1 and τ_1 :

$$\theta_j \sim N(\mu_1, \tau_1^2)$$

2. With probability p_{j2} (probability group j belongs to exchangeability set 2) θ_j follows a normal distribution with exchangeability parameters $\mu_1 < \mu_2$ and τ_2 :

$$\theta_j \sim N(\mu_2, \tau_2^2)$$

3. With remaining probability $p_{j3} = 1 - p_{j1} - p_{j2}$ (probability group j is not exchangeable with any other group), θ_j follows a weakly-informative prior distribution

$$\theta_j \sim N(m_w, v_w)$$

For the detailed specifications of m_w , v_w , the a-priori weights p_j , and the prior distributions for μ_1 , τ_1 , μ_2 , and τ_2 , see Protocol Appendix 4. At any given time of the trial, including at the end, posterior probabilities of the various parameters will be estimated using Markov chain Monte Carlo methods.

The results at the final analysis within a treatment indication will be regarded to be positive if both of the following conditions are met:

- a. posterior mean \geq “clinically meaningful activity” threshold (column for C2 in [Table 2-4](#)) (i.e. posterior mean ORR \geq C2)
- b. Posterior probability of “not being clinically meaningful” (column for C1 in [Table 2-4](#)) is less than 10% (i.e., $\text{prob}(\text{ORR} \leq \text{C1} | \text{data}) < 10\%$)

Table 2-4 Type of tumors of interest with definition of being clinically meaningful

Serial no.	Disease Code	Treatment indication	Not Clinically meaningful (C ₁)	Clinically meaningful (C ₂)
1	T5	RCC naive at 160 mg ^e	$\leq 25\%$	$\geq 37\%$
2	T12	RCC naive at 240 mg ^e	$\leq 25\%$	$\geq 37\%$
3	T11	RCC pretreated at 240 mg ^e	$\leq 10\%$	$\geq 20\%$
4	T2	Pancreatic ^b	$\leq 8\%$	$\geq 16\%$
5	T4	Urothelial ^d	$\leq 15\%$	$\geq 27\%$
6	T3	HNSCC naive ^c	$\leq 13\%$	$\geq 23\%$
7	T8	HNSCC pretreated ^c	$\leq 5\%$	$\geq 13\%$
8	T9	MSS CRC – RAS wildtype ^h	$\leq 5\%$	$\geq 13\%$
9	T10	MSS CRC – RAS mutant ^h	$\leq 5\%$	$\geq 13\%$
10	T6	TNBC ^f	$\leq 5\%$	$\geq 13\%$
11	T7	Melanoma pretreated ^g	$\leq 10\%$	$\geq 25\%$
12	T1	DLBCL ^a	$\leq 10\%$	$\geq 20\%$
13	T13	mCRPC at 240 mg ⁱ	$\leq 10\%$	$\geq 35\%$

Interim analysis will be done when at least 10 patients in any indication have at least one post-baseline assessment (except for MSS-CRC and RCC naive at 240 mg patients i.e. T9, T10 and T12, no interim analysis will be done). Extend recruitment of up to 30 patients in each treatment indication according to IA outcome [P(clinically meaningful) > 20%].
[a. Ansell et al \(2009\)](#) [b. Kunk et al \(2016\)](#) [c. Fueeder \(2016\)](#) [d. Rosenberg et al \(2016\)](#)
[e. Motzer et al \(2015\)](#) [f. Goodman \(2015\)](#) [g. Hodi et al \(2016\)](#) [h. Le et al \(2015\)](#) . [i. Bendell et al \(2019\)](#)

Details of statistical methodology :

This section provides the details of model for Part 1 of the study. Prior specifications of model parameters are provided in detail. Data analysis and decision making in real trial are illustrated using hypothetical data scenarios, see Protocol Appendix 4.

Prior specification of model parameters

Bayesian model requires prior specification of parameters. The detailed prior specification of μ_1 , μ_2 , τ_1 , τ_2 , m_w , v_w , and p_j are described in this section.

Prior specification of exchangeability distribution (μ_1 , μ_2 , τ_1 and τ_2)

Prior for τ_1 and τ_2 are assumed to be half-normal distribution with scale 0.25, implying a prior 95% intervals for τ_1 and τ_2 as (0.008, 0.560), which allows for small to substantial between-strata heterogeneity (see [Spiegelhalter et al 2004](#)).

μ_1 and μ_2 are given normal prior distributions. For first exchangeability distribution μ_1 , the mean of the prior distribution (m_{μ_1}) is set to $\text{logit}(0.15)$ (or $m_{\mu_1} = \log(3/17)$) which corresponds to no treatment effect. For second exchangeability distribution μ_2 , the prior mean (m_{μ_2}) was set to $\text{logit}(0.6)$ (or $m_{\mu_2} = \log(3/2)$). This corresponds to a substantial treatment effect. The variance parameter (V_{μ_1} and V_{μ_2}) are derived using the following formula from law of total variance

$$V_{\mu_i} = V(\theta) - E(\tau_i^2) \text{ and } V(\theta) = 1/\pi + 1/(1-\pi); \pi = 0.15, 0.60 \text{ and } i=1,2$$

This yields $V_{\mu_1} = 7.843 - 0.25^2 = 7.781$ ($\approx 2.789^2$) and $V_{\mu_2} = 4.167 - 0.25^2 = 4.104$ ($\approx 2.026^2$).

This allows a considerable uncertainty on prior belief of θ .

Prior specification for stratified or “non-exchangeability” distributions

(m_w and v_w)

The strata-specific normal priors for the stratified or “non-exchangeable” case are defined by m_w and v_w were. The prior median for the response probability was set as 10% (no treatment effect) i.e., $m_w = \text{logit}(0.1)$ (or $m_w = \log(1/9)$) and the corresponding variance (v_w) is set to 9 ($=3^2$) to allow large variability in prior.

Specification of mixture weights (p_j)

Finally, for each stratum j , the prior mixture weights p_j were chosen as

$$p_j = (0.25, 0.25, 0.50), j=1, \dots, J.$$

This means that each stratum has 25% prior probability to belong to the first exchangeability distribution (μ_1 and τ_1), 25% probability to belong to the second exchangeability distribution (μ_2 and τ_2), and 50% probability to be stratified or non-exchangeable with some (or all) of the other strata.

2.5.2.2 Part 2

Different schedules of NIR178 160 mg BID in combination with PDR001 in NSCLC will be evaluated for efficacy using ORR as the primary endpoint. The analysis is described as follows:

Overall response rate (ORR) will be provided for each schedule along with corresponding 90% confidence interval (CI). The prior distribution of ORR will be a minimally informative unimodal beta distribution with parameter $a = 1/3$ and $b = 1$ (note: this assumes a priori response rate of 25%). Posterior summaries for ORR (including 90% credible intervals and probability of ORR to fall in the activity interval defined below) will be provided.

[0, 20%): No improvement of ORR

[20%, 33%): Limited improvement of ORR

[33%, 100%]: Clinically meaningful improvement of ORR

The difference between the ORR in different schedules will be summarized.

The probability that one schedule is greater than another schedule given the data will be provided:

- i. Posterior probability that ORR for schedule 1 is greater than schedule 2
- ii. Posterior probability that ORR for schedule 2 is greater than schedule 3.
- iii. Posterior probability that ORR for schedule 1 is greater than schedule 3.

In addition, the posterior probability that ORR for one schedule is greater than the other two schedules will be provided.

The posterior mean of the differences of ORR between the schedules and the corresponding 90% credible intervals will also be provided.

2.5.2.3 Part 3

As of Protocol Amendment 6, TNBC is one of the selected treatment indications in Part 3. A second treatment indication may be considered for Part 3 after completion of Part 1. Separately from Part 1 TNBC patients (since the inclusion/exclusion criteria are different), the patients in Part 3 who will receive the new FCT formulation of NIR178 160 mg continuous dosing in combination with PDR001 will be analyzed for efficacy by treatment group using ORR as a primary endpoint with efficacy intervals as reported in [Table 2-4](#) for the TNBC group.

ORR will be provided with corresponding 90% confidence interval (CI). The prior distribution of ORR will be a minimally informative unimodal beta distribution with parameter $a = 0.176$ and $b = 1$ (note: this assumes a priori response rate of 15%). Posterior summaries for ORR (including 90% credible intervals and probability of ORR to fall in the activity interval defined below) will be provided.

[0, 5%): No improvement of ORR

[5%, 13%): Limited improvement of ORR

[13%, 100%]: Clinically meaningful improvement of ORR

2.5.3 Handling of missing values/censoring/discontinuations

At final analysis, confirmed partial or complete responses reported prior to any additional anticancer therapy will be considered as responses in the calculation of ORR irrespective of the number of missed assessments before response.

At interim analyses, patients are considered to be evaluable if they are ongoing with study treatment and have at least one post-baseline response assessment, or who have discontinued study treatment. This total will be used for percentage calculation of ORR. For the purpose of the IA, if a patient is still on study and the last available efficacy assessment is a PR/CR which is yet to be confirmed by a subsequent scan, then this patient will be considered as a responder.

For solid tumor, patients with a best overall response of 'Unknown' or 'Not Assessed' per RECIST v1.1 will be considered as non-responders and will be included in the denominator in estimating the ORR. For lymphoma, patients with unknown or missing response or who are treated in the study but provide no information on response at the end of treatment will be treated as non-responders and will be included in the denominator when calculating ORR.

2.5.4 Sensitivity analyses

Not applicable.

[REDACTED]

2.6 Analysis supporting secondary objectives

2.6.1 Efficacy objectives

The secondary objective is to assess the efficacy of NIR178 in combination of PDR001 using ORR per iRECIST, and other efficacy measures including disease control rate (DCR), duration of response (DOR), progression free survival (PFS) and 2 year overall survival (OS) by both RECIST v1.1 and iRECIST for solid tumors, by PCWG3 guidance (see Protocol Appendix 5) for mCRPC, and by [Cheson et al \(2014\)](#) for DLBCL.

These efficacy endpoints will be summarized for all the treatment groups contributing to the analysis of primary efficacy objective (see [Section 2.1](#) general analysis conventions).

ORR:

Overall response rate (ORR) is defined as the proportion of patients with best overall response (BOR) of immuno-related complete response (iCR) or immuno-related partial response (iPR), as per local review and according to iRECIST (see Protocol Appendix 3 for details) for solid tumors.

ORR as per iRECIST will be provided for each treatment indication along with corresponding 95% confidence interval (CI).

DCR:

DCR is the proportion of patients with a best overall response of CR, PR or stable disease (SD). DCR will be summarized by treatment indication with accompanying 95% confidence intervals.

OS, PFS and DOR:

OS is defined as the time from date of start of treatment to date of death due to any cause. If a patient is not known to have died, OS time will be censored at the date of last contact. The 2 year OS rate is the proportion of patients with at least 2 years of OS.

PFS is defined as the time from start of treatment date to date of the first documented disease progression or date of death, whichever happens first. If a patient has not had the event at the date of analysis cut-off, PFS will be censored at the time of the adequate tumor assessment before the cut-off.

For patients with a confirmed CR or confirmed PR, the DoR is the time from date of first documented response (CR or PR) to date of first documented progression or death due to underlying cancer, whichever happens first. If progression or death has not occurred at the date of analysis cut-off, then DoR will be censored at the date of last adequate tumor assessment before the cut-off.

Kaplan-Meier (KM) plots and estimates for time-to-event endpoints including OS, PFS, and DOR will be presented for treatment groups of size ≥ 10 patients with estimable median. Median with accompanying 90% confidence intervals along with KM estimates for PFS and OS at 4, 6, 9, 12, 18 and 24 months will be reported.

For mCRPC patients, PSA at each time-point will be listed and **change from baseline in PSA** may be plotted and summarized if there are sufficient (≥ 10) patients.

All efficacy data from the patients from Japanese safety run-in part will be listed separately. These patients will not be summarized with the other patients.

All efficacy data from the non-HNSCC patients and melanoma IO naive patients will be listed separately and will not be summarized with the other patients. All efficacy data from patients with unknown RAS status will be summarized as a separate group with all other patients using estimable endpoints (enough patients for the endpoints to be estimated); otherwise, the efficacy data will be listed.

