5.4.4 Time-to-event analyses

5.4.4.1 Progression events

iUPD should only be used for sensitivity analyses. For the primary analysis iUPD events will be treated as confirmed progression.

iPDs flagged as pPD are not included in time-to-event analyses.

Patients are classified as follows:

0	No event (censored)
1	Confirmed iPD (iCPD1 or iCPD2)
2	Unconfirmed iPD (iUPD)

For the primary analysis of time-to-event endpoints, both confirmed and unconfirmed progression will be included as progression events with date of progression being the date of the assessment flagged as iCPD1, iCPD2, or iUPD according to the algorithm defined in [Section 5.5.2](#).

A sensitivity analysis of time-to-event endpoints may be conducted in which patients with iUPD are treated as censored, with date of last adequate assessment = visit date for assessment flagged iUPD.

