5.4.4.4 Duration of response

Duration of response is defined as a time interval between the first date of confirmed iCR/iPR and the date of progression as defined in [Section 5.5.2](#). Intervening assessments of pPD are excluded from the assessment.

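### The SAP contradicts itself on what ends duration of response, so a cancer death without a progression scan is an event in one section and not in another

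*SAP*

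**What the plan says.** SAP 2.6.1 lists DoR and PFS among the measures assessed "by both RECIST v1.1 and iRECIST for solid tumors". It then defines DoR, for confirmed responders, from first documented response "to date of first documented progression or death due to underlying cancer, whichever happens first". The sentence on censoring that follows begins "If progression or death has not occurred at the date of analysis cut-off, then DoR will be censored at the date of last adequate tumor" (in effect, at the latest evaluable scan). The event sentence limits death to the cancer; the censoring sentence gives no cause. PFS in the same section ends at "date of the first documented disease progression or date of death, whichever happens first".

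The iRECIST appendix of the SAP is worded differently. Section 5.4.4.4 states: "Duration of response is defined as a time interval between the first date of confirmed iCR/iPR and the date of progression". Section 5.4.4.1 says that "both confirmed and unconfirmed progression will be included as progression events" and classes patients as having no event, confirmed progression or unconfirmed progression, with no class for death. Section 5.4.4.2 nevertheless lists the date of death among the end dates, without tying it to particular endpoints. Section 5.4.4.3 takes the censoring reasons from Protocol Appendix 2.

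Protocol Appendix 2 gives DoR the same end date and censoring as time to progression (14.2.23). That endpoint counts progression or death from the underlying cancer (14.2.21). Table 14-7, situation G, censors other deaths for these two endpoints only, and 14.2.39 lists non-cancer death as a censoring reason.

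**The concern.** DoR is a named secondary endpoint under both sets of criteria, and readers will compare the two results. If one counts a cancer death without a scan and the other does not, part of any difference comes from the definition and not from how the criteria treat pseudo-progression. Two programmers working from the same SAP could also produce different iRECIST results.

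The second matter concerns deaths from other causes. Protocol 2.6 names pneumonitis, hepatitis and severe skin reactions among the possible serious immune-mediated events. Censoring a responder who dies of such an event treats the response as one that could have continued. Whether a death is an event or a censoring turns on its attributed cause, and SAP 2.6.2.3 records the investigator as the one who selects that category.

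**Working it through.** The plan states no sample size, event count or target for DoR, so there is no figure to reproduce. The check sets the definitions side by side and then illustrates their possible size.

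**Step 1: the definitions**

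| Place | Applies to | Progression | Cancer death | Other death |
|---|---|---|---|---|
| SAP 2.6.1, DoR event sentence | RECIST v1.1 and iRECIST | event | event | not an event |
| SAP 2.6.1, DoR censoring sentence | same | – | death, no cause given | death, no cause given |
| SAP 5.4.4.4 | iRECIST DoR | event | not named | not named |
| SAP 5.4.4.2 | iRECIST time-to-event | end date | death date listed, cause not given | death date listed, cause not given |
| SAP 5.4.4.3, via Protocol 14.2.39 | iRECIST censoring | – | not a listed reason | censoring reason |
| Protocol 14.2.21, 14.2.23, Table 14-7 G | RECIST v1.1 DoR | event | event | censored |
| SAP 2.6.1, PFS | both | event | event | event |

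**Step 2: two patients**

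- A responder dies of cancer with no scan showing progression. SAP 2.6.1 gives an event at death. SAP 5.4.4.4 as worded gives none.
- A responder dies of toxicity without progression. Under 2.6.1 this is not an event. Read literally, the patient does not meet the condition for censoring either, because a death has occurred. Protocol Table 14-7 (situation G) and 14.2.39 settle it: the patient is censored at the last adequate assessment. In PFS the same patient has an event.

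**Step 3: the cross-reference**

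SAP 5.4.4.1, 5.4.4.2 and 5.4.4.4 all send the reader to Section 5.5.2 for the progression rule or date. Section 5.5.2 describes PK concentration data; the progression rules are in 5.4.2.

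**Step 4: possible size (illustration; the shares are assumed)**

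Let f be the share of first DoR events that are non-cancer deaths, and c the share that are cancer deaths without earlier documented progression. Under constant hazards the median is ln 2 divided by the total hazard. Dropping an event type therefore multiplies the median by 1/(1 − f) under 2.6.1 and by 1/(1 − f − c) under 5.4.4.4 as worded, each relative to a DoR that counts every death.

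| f | 2.6.1 | 5.4.4.4, c = 5% | 5.4.4.4, c = 10% |
|---|---|---|---|
| 5% | 1/0.95 = 1.05 | 1/0.90 = 1.11 | 1/0.85 = 1.18 |
| 10% | 1/0.90 = 1.11 | 1/0.85 = 1.18 | 1/0.80 = 1.25 |
| 20% | 1/0.80 = 1.25 | 1/0.75 = 1.33 | 1/0.70 = 1.43 |

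The gap between the two SAP definitions alone is (1 − f)/(1 − f − c). It runs from 0.95/0.90 = 1.06 to 0.80/0.70 = 1.14 over this table.

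**Step 5: small groups**

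With 30 patients at the clinically meaningful rates in SAP Table 2-4, expected responders are 30 × 0.13 = 3.9, 30 × 0.20 = 6 and 30 × 0.37 = 11.1. Take an invented set of four responders with events at 3, 5, 8 and 12 months:

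- All counted: the Kaplan-Meier curve is 0.75 at month 3 and 0.50 at month 5, so the median is 5 months.
- The month-5 event is a toxic death, censored at a scan in month 4: the curve is 0.75 at month 3 and 0.75 × 1/2 = 0.375 at month 8, so the median is 8 months.
- In addition, the month-8 event is a cancer death without a scan, censored at month 7: the curve stays at 0.75 until month 12, so the median is 12 months.

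**The case against.** A reader of 5.4.4.4 alone might infer that iRECIST DoR ignores death altogether. The SAP as a whole does not support that. Section 2.6.1 applies its cancer-death definition to iRECIST as well, 5.4.4.2 lists the date of death as an end date, and the imported censoring reason for non-cancer death makes sense for DoR only if cancer death is an event. The missing death class in 5.4.4.1 proves little: it sits under progression events and, read as literally, would remove death from iRECIST PFS too. What remains is a contradiction, not a settled exclusion.

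A reader might also infer that censoring toxic deaths is an SAP error. It is not: 2.6.1 follows Protocol Appendix 2, which states the rule in several places. Counting every death is a different choice of estimand. The SAP may make that choice, because Table 14-7 presents its first options as defaults that the protocol or SAP can override.

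The consequences are limited. DoR is descriptive, the Part 1 decision rule uses response rate alone, and SAP Section 4 reports that the study was closed for insufficient efficacy. Toxic deaths are not hidden, since PFS and OS count them and SAP 2.6.2.3 summarises and lists deaths. No rate of toxic death among responders is given, and the Amendment 6 rationale reports no hepatic adverse-event deaths to date. These points stand. They limit the weight of the finding but do not tell a programmer which event rule to use.

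**Conclusion.** The contradiction holds on the text. The SAP gives two end events for iRECIST DoR, and the censoring sentence in 2.6.1 does not match its own event sentence. The case that divides the definitions is a cancer death without a progression scan.

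Censoring non-cancer deaths is a separate, documented choice. Its weakness is that it depends on an attributed cause in an open-label trial and can overstate durability when a group has only a few responders.

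The size cannot be fixed from the documents. Step 4 rests on constant hazards and assumed shares, and the four-responder set is invented; both show what could happen, not what is expected. A fixed-time DoR percentage would be the wrong yardstick: SAP 2.6.1 plans Kaplan-Meier plots and medians for DoR, in groups of at least 10 patients with an estimable median, and sets landmark times only for PFS and OS. The primary response-rate conclusion is unaffected. This should be corrected, but it does not threaten the trial's main result.

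**What to change.** - State one DoR event definition in SAP 2.6.1 and 5.4.4.4, identical for RECIST v1.1 and iRECIST apart from how progression is determined.
- Rewrite the censoring sentence in 2.6.1 so that it matches that event and says what happens to deaths from other causes.
- Report DoR with death from any cause as an event. Either make it the main definition and list the change in SAP Section 4, or add it as a sensitivity analysis beside the cancer-death version of Appendix 2. The any-cause analysis removes the dependence on attributed cause.
- Change the Section 5.5.2 pointers in 5.4.4.1, 5.4.4.2 and 5.4.4.4 to 5.4.2. This part is clerical.

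The cost is SAP wording, one extra event flag and one extra table. DoR may look slightly shorter in the any-cause analysis.
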